12.1.1. Incidence of Treatment-Emergent Adverse Events

The TEAEs will be summarized by treatment group, SOC, PT, relationship and intensity, displaying the number and percentage of patients with at least one TEAE using only the worst intensity recorded at each level of summarization. The total number of events and number and percentage of patients with at least one TEAE over all SOCs will also be displayed.

12.1.2. Serious Adverse Events

A serious adverse event (SAE) is defined as any event that results in death, is life threatening, requires inpatient hospitalization or prolongation of existing hospitalization, results in persistent or significant disability/incapacity, or is a congenital anomaly/birth defect. Medical and scientific judgment should be exercised in deciding whether expedited reporting is appropriate in other situations, such as important medical events that may not be immediately life-threatening or result in death or hospitalization but may jeopardize the patient or may require medical or surgical intervention to prevent one of the outcomes listed in the definition above. These should also be considered serious.

The TESAE will be summarized by treatment group, SOC, PT, relationship and intensity, displaying the number and percentage of patients with at least one TESAE using only the most severe intensity recorded at each level of summarization. The total number of events and number and percentage of patients with at least one TESAE over all SOCs will also be displayed. All SAEs including serious criteria and SAE description will be presented in an additional information listing.

12.1.3. Deaths

All patients who have a SAE with serious criteria of “Death” will be presented in a listing and

the following variables will be included; date of study drug administration, date of last visit, date of death, time (days) to death from study drug administration, TEAE flag, SOC/PT, whether an autopsy was performed (no, yes), whether a death certificate was completed (no, yes), relationship to study drug. Time (days) to death from study drug administration will be calculated as (date of death – date of study drug administration + 1).

12.1.4. Treatment-Emergent Adverse Events Leading to Discontinuation

All patients who have a TEAE with an action taken with study drug of “Drug Withdrawn” will be summarized by treatment group, SOC, PT, relationship and intensity, displaying the number and percentage of patients with at least one TEAE leading to study drug discontinuation, using only the most severe TEAE recorded at each level of summarization. The total number of events and number and percentage of patients with at least one TEAE which led to study drug discontinuation over all SOCs will also be displayed.

12.1.5. Treatment-Emergent Adverse Events of Special Interest

The AEs checked as “Yes” to “Is Adverse event classified Infusion Related Reactions including Hypersensitivity and Anaphylactic Reactions?” on the “Adverse Event” page of eCRF will be classified as Infusion Related Reaction (IRR) including Hypersensitivity and Anaphylactic Reaction, and considered as adverse events of special interest (AESI) because AE related to infusion related reactions (hypersensitivity/anaphylactic reactions).

TEAEs of special interest (TEAESI; IRR including hypersensitivity/anaphylaxis reaction) will be summarized by treatment group, SOC, PT, relationship and intensity, displaying number and percentage of patients with at least one TEAESI using only the most severe TEAESI recorded at each levels of summarization. The total number of events and number and percentage of patients with at least one TEAESI over all SOCs will also be displayed. Additionally, table for signs and symptoms of TEAESI will be provided separately by SOC, PT and intensity.

Experienced signs and symptoms of TEAESI will be presented in additional information listings for TEAESI.

12.2. Clinical Laboratory Evaluations

Blood and urine samples for clinical laboratory assessments including clinical chemistry, hematology, and urinalysis will be collected at the time points specified in [Appendix 1](#) and [Appendix 2](#). Laboratory analyses will be performed by the local laboratories. For the first CSR, results will be listed based on local laboratories units. Results converted to International System of Units (SI units) will be listed and summarized in the Final CSR. The results in local unit that cannot be converted to SI unit are collected, the results will be listed and summarized separately in local unit in the Final CSR.

The following clinical laboratory assessments will be performed:

Clinical chemistry:	Total protein, serum bilirubin (total, direct), ALT, AST, alkaline phosphatase, γ -glutamyl transferase, blood urea nitrogen, creatinine,
---------------------	--

creatine kinase, creatine kinase-myocardial band isoenzyme, troponin (I or T, [only one applicable]), albumin, sodium, potassium, calcium, chloride, inorganic phosphorus, glucose, lactate dehydrogenase, total cholesterol, triglyceride, high-density lipoprotein cholesterol, and CRP

Hematology: Red blood cells, erythrocyte sedimentation rate, total white blood cell count, absolute neutrophil count, eosinophil count, lymphocyte count, platelet count, hemoglobin, mean corpuscular volume, mean corpuscular hemoglobin, mean corpuscular hemoglobin concentration, and hematocrit

Urinalysis: Bilirubin, blood, glucose, ketones, leukocytes, nitrite, pH, protein, specific gravity, urobilinogen, and microscopic examination of white blood cell count, red blood cell count, and bacteria

Abnormal clinical laboratory values will be flagged as either “High” or “Low” based on the reference ranges for each laboratory parameter. The investigator will determine whether any of the abnormal clinical laboratory values are clinically significant or not clinically significant.

Some numeric parameters will be labeled with a CTCAE term, and grading will be applied to post-baseline values for numeric parameters where possible according to CTCAE version 5.0. Grades that require clinical input only will not be assigned to these parameters. Grades which are part numeric and part clinical input will be assigned based on the numeric portion only. If different grades share the same criteria due to exclusion of clinical input, lower grade will be used. The CTCAE terms and grades for applicable parameters are listed in [Appendix 4](#). The CTCAE grades for this analysis will be Grade 1 (Mild), Grade 2 (Moderate), Grade 3 (Severe) and Grade 4 (Life-threatening). The CTCAE Grade 5 (Death) will not be applied in this analysis since death cannot be determined from a numeric laboratory result. If the post-baseline result for a patient does not satisfy any CTCAE grade, it will be classified as “No Grade”.

Actual results and changes from baseline of numeric laboratory parameters including clinical chemistry, hematology, and urinalysis will be summarized using descriptive statistics by treatment group, parameter and scheduled visit in separate tables by laboratory category. For the purpose of summarization, any numeric values recorded from the clinical laboratory tests which are below the lower limit or above the upper limit of quantification will be set to the respective limit for all related summaries. In listings, original results containing inequality signs will be displayed.

The number and percentage of patients for clinical laboratory test results (clinical chemistry, hematology, and urinalysis) will be summarized using {“Normal”, “Abnormal, Not Clinically Significant”, “Abnormal, Clinically Significant”} categories as appropriate, by treatment group, parameter and visit, in the form of a shift table to detect changes from baseline, in separate tables by laboratory category.

The number and percentage of patients with a result for each CTCAE grade will be summarized by treatment group, laboratory category, CTCAE term and scheduled visit. Additional tables

will be generated using the most severe grade after study drug administration. The most severe grade will be selected including all post-baseline scheduled and unscheduled visits.

All clinical laboratory test results of clinical chemistry, hematology, and urinalysis will be presented in separate listings by laboratory category. For values that are outside the normal range, high and low flags and clinical significance as evaluated by the investigator will be presented if applicable, and CTCAE results will also be presented for applicable parameters.

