### **4.3 Exclusion Criteria**

A patient meeting any of the following criteria will be excluded from the study:

1. Patient with severe condition meeting one of the following:
  - a. Respiratory distress with respiratory rate  $\geq 30$  breaths/min.
  - b. Requires supplemental oxygen.
  - c. Experience shock.
  - d. Complicated with other organs failure, and intensive care unit monitoring treatment is needed by investigator's discretion.
  - e. Any other conditions suspected of being severe symptoms of SARS-CoV-2 infection, in the opinion of the investigator, including but not limited to radiographic findings in lung.
2. Patient has a medical history or current presence of disease including one or more of the following(s):
  - a. Clinical hematology results of neutrophil count  $< 1.0 \times 10^3$  cells/ $\mu$ L (International System of units  $< 1.0 \times 10^9$  cells/L) at Screening and Day 1.
  - b. Clinically significant condition of allergic reaction (e.g., urticaria, angio-oedema), atopic condition (asthma and eczematous dermatitis) in the investigator's opinion

and/or hypersensitivity including known or suspected clinically relevant drug hypersensitivity to any monoclonal antibody or any components of study drugs.

- c. History of and/or current medical condition, classed as clinically significant by the investigator, including gastrointestinal, renal, endocrine, neurologic, autoimmune, hepatic, hematological, metabolic (including known diabetes mellitus), cardiovascular, or psychiatric condition.
- d. History or any concomitant active malignancy.
- e. History of and/or current infection with human immunodeficiency virus (HIV), hepatitis B or hepatitis C.
- f. History of serious infection (associated with hospitalization and/or which required intravenous antibiotics) within 6 months before the study drug administration and/or current infection, other than SARS-CoV-2 infection, requiring a course of systemic anti-infective therapy.
- g. History of an illness, other than SARS-CoV-2 infection, within 28 days prior to the study drug administration that is identified as clinically significant by the investigator and/or requires hospitalization.
- h. History of surgical intervention and/or an operation within 28 days prior to the study drug administration or plans to have a surgical procedure during the study period.

3. Patient had a history of or concurrent use of medications including any prior therapy of following(s):

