5.5. Definition of Baseline

The baseline value will be considered to be the last non-missing value before the study drug administration. Post-baseline values will be considered to be all measurements collected after the study drug administration.

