Hyponatremia	Sodium	Low	<LLN - 130 mmol/L	125-129 mmol/L	120-124 mmol/L regardless of symptoms	<120 mmol/L

Cholesterol high	Total Cholesterol	High	>ULN - 300 mg/dL; >ULN - 7.75 mmol/L	>300 - 400 mg/dL; >7.75 - 10.34 mmol/L	>400 - 500 mg/dL; >10.34 - 12.92 mmol/L	>500 mg/dL; >12.92 mmol/L
Neutrophil count decreased	WBC Differential, Neutrophils	Low	<LLN - 1500/mm ³ ; <LLN - 1.5 x 10 ⁹ /L	<1500 - 1000/mm ³ ; <1.5 - 1.0 x 10 ⁹ /L	<1000 - 500/mm ³ ; <1.0 - 0.5 x 10 ⁹ /L	<500/mm ³ ; <0.5 x 10 ⁹ /L
Hypertriglyceridemia	Triglyceride	High	150 mg/dL - 300 mg/dL; 1.71 mmol/L - 3.42 mmol/L	>300 mg/dL - 500 mg/dL; >3.42 mmol/L - 5.7 mmol/L	>500 mg/dL - 1000 mg/dL; >5.7 mmol/L - 11.4 mmol/L	>1000 mg/dL; >11.4 mmol/L

LLN = lower limit of normal, ULN = upper limit of normal.

1) The most severe grade is counted if the CTCAE grade is discrepant by multiple definitions.

Note: The LLN and ULN values will be the lower and upper limits of the normal ranges as provided by the local laboratory at each relevant transfer. In case numeric value for grading is identical such as Hypokalemia, CTCAE grade which includes numeric value will only be applied, because abnormal laboratory value with clinical input was reported as an adverse event and graded accordingly. @ indicates that corrected calcium (mg/dL) = measured total calcium (mg/dL) + 0.8 (4.0 – serum albumin [g/dL]), where 4.0 represents the average albumin level. For SI units as: Corrected calcium (mmol/l) = total Ca (mmol/l) + 0.02 (40 –serum albumin [g/l]).

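### Laboratory CTCAE grades are planned for post-baseline values only, so for 18 of 26 terms the Final CSR grade tables alone cannot tell an abnormality present before dosing from a post-dose worsening

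*SAP*

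**What the plan says.** SAP 12.2 sets the scope of grading: "grading will be applied to post-baseline values for numeric parameters where possible according to CTCAE version 5.0". A post-baseline value that meets no grade is classed as No Grade. Two displays follow:

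- **By visit.** Counts and shares are planned; the SAP states that "patients with a result for each CTCAE grade will be summarized by treatment group, laboratory category, CTCAE term and scheduled visit".
- **Worst grade.** Further tables "will be generated using the most severe grade after study drug administration", taken over scheduled and unscheduled post-baseline visits.

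Neither display carries a baseline grade. The same section plans other summaries that do use baseline:

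- "Actual results and changes from baseline of numeric laboratory parameters including clinical chemistry, hematology, and urinalysis will be summarized using descriptive statistics".
- A table with the categories Normal, Abnormal Not Clinically Significant and Abnormal Clinically Significant, "in the form of a shift table to detect changes from baseline, in separate tables by laboratory category".
- Listings of all results, with high/low flags, clinical significance and CTCAE results where applicable.

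SAP 5.5 defines baseline: "The baseline value will be considered to be the last non-missing value before the study drug administration". SAP Appendix 4 gives the numeric limits for each term.

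**The concern.** Every patient enters with an acute SARS-CoV-2 infection, so some laboratory values may be outside their limits before any drug is given. Where a grade depends only on a fixed cut-off or a normal-range limit, such a patient receives the same grade after dosing even if nothing has changed. The worst-grade table makes this more likely, because it takes the maximum over all post-dose samples and laboratory sampling starts on Day 2. A patient whose count recovers by Day 7 still keeps the Day 2 grade.

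The table also mixes two rules without saying so. An unchanged abnormal ALT gives No Grade, while an unchanged low lymphocyte count gives a grade. What is at stake is how the Final CSR laboratory grade tables are read in a study with 5 CT-P59 patients per dose and 3 pooled placebo patients.

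**Working it through.** No figure in the plan is disputed. The check is a count of terms, the grading rules applied to example values, and an illustration of size.

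**1. Appendix 4 terms by use of baseline**

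| Basis of grade | Terms | Count |
|---|---|---|
| Uses the patient's baseline | ALT, AST, ALP, GGT, bilirubin, eosinophilia, hemoglobin increased | 7 |
| Mixed | Creatinine (Grade 1 rests on ULN alone; Grades 2 and 3 accept a multiple of baseline or of ULN) | 1 |
| Fixed or LLN/ULN limits only | Hypoalbuminemia, leukocytosis, WBC decreased, hypercalcemia, hypocalcemia, hypoglycemia, anemia, LDH increased, lymphocytes decreased, lymphocytes increased, platelets decreased, hyperkalemia, hypokalemia, hypernatremia, hyponatremia, cholesterol high, neutrophils decreased, hypertriglyceridemia | 18 |

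7 + 1 + 18 = 26.

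**2. An overlap that needs no assumption**

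Protocol 4.3, criterion 2a ("Clinical hematology results of neutrophil count"), excludes only counts below 1.0 x 10^9/L. The Appendix 4 entry "Neutrophil count decreased" makes values from 1.0 to below 1.5 x 10^9/L Grade 2. A patient with 1.2 x 10^9/L passes this criterion. If the count stays at 1.2, or rises to 1.4, the patient is tabulated as post-dose Grade 2.

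**3. The two rules side by side** (assumed limits: lymphocyte LLN 1000/mm3, ALT ULN 40 U/L, bilirubin ULN 1.2 mg/dL)

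| Parameter | Before | After | Post-dose grade |
|---|---|---|---|
| Lymphocytes | 700 | 700 | 2 |
| Lymphocytes | 700 | 780 (improving) | 2 |
| ALT | 90 | 90 | No Grade |
| Bilirubin | 2.0 | 2.0 | No Grade |

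**4. Weight of one patient**

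There are 3 cohorts of 5 CT-P59 plus 1 placebo, so 3 x 6 = 18, which agrees with the stated sample size. Pooled placebo is 3 x 1 = 3. One patient is 1/5 = 20 percentage points of a dose group, or 1/3 = 33 points of placebo.

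**5. Illustration of size**

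The documents give no share p of patients with a gradeable abnormality before dosing. Assume 5% to 40% for one affected term, independent patients, no drug effect, and an abnormality that persists to at least one post-dose sample.

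- At least one graded patient in a dose group: 1 - (1 - p)^5
- Expected graded patients among 15 on CT-P59: 15p
- None of 3 on placebo and at least one of 15 on CT-P59: (1 - p)^3 x [1 - (1 - p)^15]

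| p (assumed) | At least 1 of 5 | Expected of 15 | 0 of 3 and at least 1 of 15 |
|---|---|---|---|
| 5% | 22.6% | 0.75 | 46.0% |
| 10% | 41.0% | 1.5 | 57.9% |
| 20% | 67.2% | 3.0 | 49.4% |
| 30% | 83.2% | 4.5 | 34.1% |
| 40% | 92.2% | 6.0 | 21.6% |

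**6. Whether baseline grading can be extended to all terms**

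It cannot. With ALT ULN 40, a baseline of 130 is 130/40 = 3.25 x ULN, Grade 2 by the ULN limits. A post-dose value of 250 is 250/130 = 1.9 x baseline, Grade 1 by the abnormal-baseline rule. A grade shift would show improvement while ALT nearly doubled.

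Creatinine does not have this problem. Appendix 4 counts the more severe grade when its definitions disagree, so the post-dose grade is never below the ULN-based grade. A rising value therefore cannot appear as a falling grade.

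**The case against.** The strongest reply is that nothing in the plan treats these grades as drug toxicity, and that pre-dose abnormality is visible elsewhere. Most of this stands.

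- **Not labelled toxicity or treatment-emergent.** A reader might infer that abnormalities present before dosing are counted as toxicity. The SAP does not say so. Adverse events follow their own rules: under Protocol 6.1.1.1.6, a condition present at screening that does not deteriorate is not reported as an AE. The stopping rules in Protocol 3.3.2 use related TEAEs and TESAEs, not these tables.
- **Not a Day 14 result.** Laboratory tests are a primary endpoint analysed on data to Day 14 (Protocol 2.2.1), so a reader might infer that the primary safety report is distorted. SAP 12.2 only lists laboratory results in the first CSR, and Appendix 5 contains the three laboratory listings but no laboratory summary or CTCAE table.
- **Other outputs use baseline.** Change from baseline and the listings let a reader check any graded patient's pre-dose value, which is feasible with 18 patients. It would be wrong to say that the whole plan cannot distinguish disease at entry from later change.
- **Equal in expectation.** Randomised placebo patients carry pre-dose abnormalities too, so there is no systematic tilt between arms. Exclusion 2c may also reduce some of these abnormalities at entry.

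What the reply does not remove is the gap in the grade tables themselves. Group mean changes do not identify patients. The three-category shift table puts Grade 1 to Grade 3 and Grade 3 to Grade 3 in the same abnormal-to-abnormal cells when the clinical-significance category is the same. Pre-dose rows in the listings carry no grade, so the reader must assign it by hand.

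**Conclusion.** The point holds for 18 of the 26 Appendix 4 terms and for creatinine Grade 1. For these, an unchanged or improving pre-dose abnormality is tabulated as a post-dose grade in the Final CSR by-visit and worst-grade tables, and those tables alone cannot separate it from a worsening. The same gap can hide a true rise in grade. The 7 baseline-referenced terms, including the liver tests, are not affected.

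The size is not known. The 20 and 33 percentage points are the weight of one patient in any table of this trial, not an estimate of bias, and the probabilities above depend on an assumed prevalence of 5% to 40%. They show only that, in groups of 5 and 3, chance imbalance in pre-dose abnormality can easily resemble a difference between CT-P59 and placebo. The documents do not support a claim that the TEAE counts, the escalation decisions or the Day 14 report are distorted by these tables. This is a modest weakness in presentation that is worth correcting before the Final CSR.

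**What to change.** Amend SAP 12.2 as follows:

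1. For the 18 terms without a baseline reference, and for creatinine by its ULN limits, also assign an Appendix 4 grade to the baseline value defined in SAP 5.5.
2. For these terms, present the worst-grade table as baseline grade by worst post-baseline grade. Its margin keeps the worst-grade counts already planned. Flag patients whose grade rises above baseline.
3. Add the baseline grade as a row in the by-visit grade table.
4. Leave the 7 baseline-referenced terms as they are, for the reason shown by the ALT example, and say in a footnote which terms follow which rule.
5. Keep the change-from-baseline summaries and the listings, so that worsening within a grade (for example lymphocytes from 790 to 510/mm3, both Grade 2) stays visible.

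The cost is a few sentences in the SAP and a little more table programming. Screening and Day 1 predose samples are already scheduled, so no new data, visits or patients are needed.

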12.3. Vital Signs and Weight

Vital signs and weight measurements will be performed at the time points specified in [Appendix 1](#) and [Appendix 2](#). Vital signs (including systolic and diastolic blood pressures, heart rate, respiratory rate, body temperature and SpO₂) will be measured after the patient has rested quietly for at least 5 minutes. SpO₂ will be measured while breathing normal room air. Body temperature will be measured using tympanic thermometer throughout the study.

All vital signs will be summarized using descriptive statistics of actual result and change from baseline by treatment group, parameter and scheduled visit. All vital signs and weight except for hypersensitivity monitoring results will be listed for each patient by treatment group, parameter and visit.

12.4. Hypersensitivity Monitoring

For hypersensitivity monitoring, additional vital signs measurements including systolic and diastolic blood pressure, heart rate, respiratory rate and body temperature will be performed at the following time points in [Table 5](#).

Table 5 Schedule of Assessments for Hypersensitivity Monitoring

Day	Time points	Window
Day 1	Pre-dose	Within 30 minutes
	15 minutes from start of infusion	± 5 minutes
	30 minutes from start of infusion	
	60 minutes from start of infusion	
	90 minutes from start of infusion	
	2 hours from start of infusion	± 15 minutes
	3 hours from start of infusion	
	6 hours from start of infusion	
12 hours from start of infusion		
Day 2	24 hours from start of infusion	± 30 minutes

The number and percentage of patients who have clinically notable hypersensitivity result will be summarized in a table by treatment group, scheduled time points and parameter. The criteria for clinically notable results are defined as follows in [Table 6](#).

Table 6 Hypersensitivity Classification for Vital signs

Parameter	Low	High
Systolic blood pressure (mmHg)	≤ 90	≥ 160
Diastolic blood pressure (mmHg)	≤ 50	≥ 90
Heart rate (beats per minute)	≤ 50	≥ 100
Respiratory rate (breaths per minute)	≤ 12	≥ 20
Body temperature (°C)	≤ 35.0	≥ 38.0

All vital signs data for hypersensitivity monitoring will be listed for each patient by treatment group, time point and parameter. High and low flags will also be presented in the listing to show whether a hypersensitivity result is outside of normal range.

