## **2.2 Study Endpoints**

### **2.2.1 Primary Endpoints**

Primary endpoints will be analyzed based on the data up to Day 14 of the last enrolled patient.

- Treatment-emergent adverse events (TEAEs)
- Treatment-emergent serious AEs (TESAEs)
- Treatment-emergent AEs of special interest (TEAESI; infusion related reactions including hypersensitivity/anaphylactic reaction)
- Potential effects on the incidence of antibody-dependent enhancement (ADE)
- Vital signs (blood pressure, heart rate, body temperature, SpO2 and respiratory rate)
- Hypersensitivity monitoring
- Twelve-lead electrocardiogram (ECG)
- Severe Acute Respiratory Syndrome Coronavirus infection related signs and symptoms
- Radiography (chest x-ray and/or chest CT)
- Clinical laboratory test (clinical chemistry, hematology, and urinalysis)

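### The hypersensitivity vital-sign table applies fixed limits without using the same patient's pre-dose reading, so abnormality already present before infusion can be counted after it under a hypersensitivity label

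*SAP*

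**What the plan says.** Protocol 2.2.1 lists "Hypersensitivity monitoring" among the primary safety endpoints.

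SAP 12.4 has two parts. Table 5 ("Schedule of Assessments for Hypersensitivity Monitoring") sets a Day 1 pre-dose reading within 30 minutes, then nine readings timed from the start of infusion: 15, 30, 60 and 90 minutes, and 2, 3, 6, 12 and 24 hours. Table 6 ("Hypersensitivity Classification for Vital signs") then sets the rule: "The criteria for clinically notable results are defined as follows in" that table. Its limits are absolute:

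- systolic pressure 90 or below, 160 or above (mmHg)
- diastolic pressure 50 or below, 90 or above (mmHg)
- heart rate 50 or below, 100 or above (beats/min)
- respiratory rate 12 or below, 20 or above (breaths/min)
- temperature 35.0 or below, 38.0 or above (°C)

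The summary is: "The number and percentage of patients who have clinically notable hypersensitivity result will be summarized in a table by treatment group", scheduled time point and parameter. For the listing: "High and low flags will also be presented in the listing to show whether a hypersensitivity result is outside of normal range".

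Neither output refers to the patient's pre-dose value, although SAP 5.5 defines baseline as the last value before study drug.

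**The concern.** The label says hypersensitivity, but the rule measures only whether a vital sign lies outside a fixed range at that moment. In healthy volunteers the two might nearly coincide. Here the patients have a symptomatic respiratory infection that can itself raise temperature, breathing rate and heart rate.

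A count after the start of infusion can therefore mix two kinds of patient: those who became abnormal after infusion began, and those who were abnormal already. Only the first kind bears on an infusion effect. With groups of 5, 5, 5 and 3, one patient of the second kind visibly changes a percentage.

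The same rule can also hide a change. If one patient's flag clears and another's appears, the count stays the same.

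**Working it through.** The documents give no rate, power or error level for this table, so there is no planned figure to reproduce. The check sets the sections side by side and then sizes the effect.

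**1. Can a patient meet a limit before dosing?**

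- Respiratory rate: Protocol 4.3, exclusion 1a, is "Respiratory distress with respiratory rate" of 30 breaths/min or more, and this is the only numerical limit on breathing rate. Values of 20 to 29 are not excluded by it and already meet the Table 6 High limit. Whole-number values of 13 to 19 are the only unflagged ones.
- Temperature: Protocol 4.2 sets no ceiling. Feeling feverish is one of seven symptoms that qualify a patient if present in the 48 hours before dosing. Shortness of breath is another.

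So the answer is yes, it can happen. The documents do not say how often.

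**2. Does a pre-dose row solve it?** Take a group of 5 showing 1/5 flagged pre-dose and 1/5 at 30 minutes. This could be one patient with a stable fever. It could equally be one patient who settled and another who became newly abnormal. The rows are identical and the meanings differ. The stated breakdown also does not mention direction: a diastolic pressure of 92 pre-dose and 48 during infusion would count once at each time, unless the table shells separate Low from High.

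**3. How does the SAP treat comparable data?** Shift tables from baseline are planned for laboratory results (12.2), ECG (12.5), physical examination (12.6), radiography (12.8) and respiratory signs (12.10). SAP 12.3 plans change from baseline for vital signs. SAP 12.4 states neither.

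**4. Size of one patient.** Group sizes from SAP 4.1: 5 on CT-P59 and 1 on placebo in each of 3 cohorts, with placebo pooled.

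- CT-P59 group: 1/5 = 20 percentage points.
- Pooled placebo: 1/3 = 33 percentage points.

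**5. Chance of at least one such patient.** Let q be the assumed share of patients past a limit from infection alone. The chance is 1 − (1 − q)^n.

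| q (assumed) | n = 5 | n = 3 |
|---|---|---|
| 10% | 41% | 27% |
| 20% | 67% | 49% |
| 30% | 83% | 66% |
| 50% | 97% | 88% |

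For q = 20%: 1 − 0.8^5 = 0.672 and 1 − 0.8^3 = 0.488.

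**6. What the pre-dose link changes at one time point, with no drug effect.** This is an illustration; the means and SDs are assumed. Each patient has a normally distributed true level b, and readings scatter normally around it. With g(b) the chance that a reading is flagged, the current rule gives E[g] and the newly notable rule gives E[g(1 − g)].

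| Parameter (between-, within-patient SD) | Mean | Current rule | Newly notable |
|---|---|---|---|
| Temperature (0.5, 0.25 °C) | 36.8 | 1.6% | 1.0% |
| | 37.3 | 10.5% | 4.5% |
| | 37.8 | 36.0% | 9.5% |
| Respiratory rate (2, 1 breaths/min) | 16 | 7.3% | 3.9% |
| | 18 | 18.9% | 7.0% |
| | 20 | 50.2% | 10.4% |

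These are simulated values. A numerical integration of the same model agrees to within 0.2 percentage points. The link matters more the closer patients start to a limit. It does not remove every chance or disease-related crossing.

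**The case against.** **The data are not lost.** With about 18 patients, the listing gives every hypersensitivity reading by patient, time point and parameter, so pre-dose and later status can be read directly. This stands, and it limits the point to the summary table and its label.

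**Safety decisions do not rest on Table 6.** Adverse events of special interest come from the investigator's eCRF classification (SAP 12.1.5), with a separate signs-and-symptoms table. The stopping rules (Protocol 3.3.2) use related treatment-emergent events. This stands.

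**The table is not in the Day 14 report.** SAP Appendix 5 includes the hypersensitivity vital-signs listing (16.2.9.2) but no count table. This stands, and it qualifies the primary-endpoint status.

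**Change from baseline may already be planned.** SAP 12.3 covers all vital signs and excludes hypersensitivity readings only in its listing sentence. However, its summary is by scheduled visit, and nine of the ten Table 5 times fall on Day 1. Whether those readings are covered is unclear.

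**Entry is not wide open.** Exclusion 1e lets the investigator exclude suspected severe disease, oxygen saturation must be at least 94%, and feeling feverish is a reported symptom, not a measured temperature. Being flagged before dosing is therefore possible, not established as common. Nor must such a patient be flagged at every later time: readings vary, so the patient may be flagged again.

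**A large pooled percentage is tempting but does not measure this flaw.** A reader might pool 9 times × 5 parameters = 45 readings and compute 1 − (1 − p)^45. At p = 2% per independent reading this is 59.7%, and at 5% it is 90.1%. The SAP plans no such pooled statistic, p is not in the documents, and independence contradicts the idea of a persistent flag. Requiring an unflagged pre-dose value for that parameter gives 1 − [1 − (1 − p)(1 − (1 − p)^9)]^5 = 58.9% and 88.5%. It barely moves, so the figure reflects the number of readings and not the missing pre-dose link.

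**Conclusion.** The point holds as a weakness of one descriptive table. Table 6 counts absolute values, the pre-dose reading is collected but not used in the rule, and the population can meet a limit before dosing. Counts after the start of infusion can therefore include pre-existing abnormality under a hypersensitivity label, and a marginal pre-dose row cannot separate persistent from new flags.

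The size that follows from the documents alone is 20 percentage points per affected patient in a CT-P59 group and 33 in pooled placebo. How many patients would be affected is not known; the percentages in steps 5 and 6 rest on assumed inputs.

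A reader might infer that the table chiefly records COVID-19, or that the trial can neither show nor rule out an infusion effect. The documents support neither. No pre-dose flag rate is given, the patient-level listing shows each pre-dose value, and infusion reactions are captured separately as adverse events. The change is worth making because it alters what the table reports at little cost.

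**What to change.** In SAP 12.4, replace or supplement the Table 6 count as follows, by treatment group, time point and parameter:

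1. A shift from the patient's own pre-dose category (Low, within limits, High) to the category at each later time.
2. Within that table, the number newly notable, separately for Low and High.
3. Descriptive change from the pre-dose value. Without it, a patient already flagged before dosing could worsen and never appear as newly notable in that direction.
4. A neutral label, such as *notable vital sign during hypersensitivity monitoring*.

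Keep the absolute flags in the listing and leave the Table 6 cut-offs unchanged. State in SAP 12.3 whether its change-from-baseline summary includes the Table 5 readings.

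Cost: one derived variable and one small table. The pre-dose reading is already scheduled, so no new data or visits are needed.
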